7.2.4 EARLY TERMINATION

Premature termination of a subject from the study will be considered clinically appropriate for any of the following reasons: (1) significant side effects from the study medication; (2) serious or unexpected AEs; (3) inability to comply with the study protocol; (4) protocol violation; or (5) emergence of serious medical or psychiatric illness.

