1. ABSTRACT/STUDY DIAGRAM

Most cocaine dependent patients suffer from deficits in cognitive function that, if left untreated, predict poor outcome.

Purpose: The present study investigates a pharmacotherapeutic intervention designed to improve cocaine treatment success by combining medications that act simultaneously on dopamine, the brain system that is critically associated with chronic cocaine use and cognitive functions. **Procedures:** Treatment with levodopa/carbidopa plus ropinirole (tested at two doses) will be compared to levodopa/carbidopa alone, and placebo. Measurement of performance on behavioral/cognitive measures of decision-making, behavioral inhibition, reward motivation, and attentional bias will be conducted at treatment entry and at repeated time points during the 10-week treatment. It is hypothesized that treatment with levodopa/carbidopa + ropinirole will produce superior outcomes in terms of reduced cocaine use and increased treatment retention and that these effects will occur indirectly via improved performance on observed cognitive mechanisms. **Course of Study:** Eligible cocaine dependent patients will be randomized equally to one of four medication conditions. Outpatient treatment will last 10 weeks and consist of thrice-weekly clinic visits. The behavioral therapy platform for this trial will consist of weekly cognitive behavioral therapy (CBT). The primary outcome measure will be weekly mean proportion of cocaine non-use days. Secondary endpoints will include abstinence rates during the last 2 weeks of treatment, time in study, and medication compliance. **Enrollment:** This project requires a final intent-to-treat sample size of 200 subjects. To obtain this sample, we expect to conduct phone screens on ~ 640 individuals, of whom 320 (50%) will qualify, enroll, and start intake. Of the 320 who start intake, we expect that 200 (~60%) will complete intake and be randomized into the ITT sample. Based on these projections and recruitment rates achieved during our previous levodopa studies, 40 months will be allotted to complete study enrollment (~ 5 new subjects/month).

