7.2.3 IN TREATMENT

During the 9-week treatment phase participants will be scheduled to attend three clinic visits per week (MWF). Activities conducted at these visits will include urine testing, administration of study medication, cognitive behavioral therapy, and prize-based CM for attendance. Brief (5-10 min) evaluations by the study nurse will be conducted weekly to address concerns related to side effects, concomitant medications, and general adherence to the medication regimen.

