7.2.4 COMPENSATION SCHEDULE

Participants will receive \$50 for completing the intake assessment phase of this study. Weekly assessments during treatment will take approximately 20 minutes to complete. Participants will earn prize bowl draws each time they attend a clinic visit (MWF) and provide a usable urine specimen. The prize-based CM is explained above (see Sect. 6.5). Behavioral tasks at Weeks -1, 3, 5, 7, and 9 will take approximately 65 minutes to complete. Participants will receive an additional \$25 (gift card) for each of these assessments, plus any task-specific earnings (approx. \$8). Subjects will also receive \$5 for each medication pack returned and bus/parking tokens as needed.

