7.2.5 END OF STUDY VISIT (WEEK 9)

At week 9, participants will be administered end of study assessments and given appropriate referrals to alternative treatment facilities in the area.

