 $[\text{levodopa}/\text{carbidopa} + 4 \text{ mg/d ropinirole}] > [\text{levodopa}/\text{carbidopa} + 2 \text{ mg/d ropinirole}] > [\text{levodopa}/\text{carbidopa} + \text{placebo}] > [\text{placebo} + \text{placebo}]$. H1 will test for differential change over time as a function of treatment. H2 will test the ordinal relations of treatment effects as a follow-up analysis. As defined above (see Sect. B.3.2.5.ii) cocaine use will be measured by urine benzoylecgonine and by the SPRHK1 approach. Generalized linear mixed models will evaluate the probability of cocaine use as a function of time, treatment and their interaction. Logistic regression will evaluate retention, defined by completion of 12 weeks of treatment, as function of intervention condition. Proportional hazards regression will evaluate time to drop-out as a function of treatment. If differential attrition raises concerns regarding non-ignorable missingness, evaluation of cocaine use will implement pattern-mixture modeling. To evaluate the relative efficacy of the treatment conditions we will follow up the omnibus test with ordinal contrasts.

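### Early termination removes a participant from the study rather than only from study drug, and nothing provides for collecting cocaine-use data afterwards

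*Protocol*

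**What the plan says.** The second protocol section numbered 7.2.4, Early Termination, reads: "Premature termination of a subject from the study will be considered clinically appropriate for any of the following reasons: (1) significant side effects". The list continues with serious or unexpected adverse events, inability to comply, protocol violation and emerging serious illness. All five reasons lead to one action, which is leaving the study.

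The other relevant text is as follows.

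- **Analysis sample (Abstract).** "This project requires a final intent-to-treat sample size of 200 subjects". The primary outcome is the weekly mean proportion of days without cocaine use. "Secondary endpoints will include abstinence rates during the last 2 weeks of treatment, time in study, and medication compliance".
- **Where urine is collected (7.2.3).** "Activities conducted at these visits will include urine testing, administration of study medication, cognitive behavioral therapy, and prize-based CM for attendance".
- **Incentive (7.2.4, Compensation Schedule).** "Participants will earn prize bowl draws each time they attend a clinic visit (MWF) and provide a usable urine specimen".
- **Final assessment (7.2.5).** "At week 9, participants will be administered end of study assessments". The section does not mention participants terminated earlier.
- **Schedule (section 8).** Urine tests and the SUR form (not spelled out; taken here to be the substance-use report) are listed three times a week from the admit week to week 10. There is no early-termination or off-drug column.
- **Tolerability (6.4).** In the high-dose arm, ropinirole may be held at 2 mg/d.
- **Analysis (SAP, Primary Hypothesis Testing).** "Generalized linear mixed models will evaluate the probability of cocaine use as a function of time, treatment and their interaction". "If differential attrition raises concerns regarding non-ignorable missingness, evaluation of cocaine use will implement pattern-mixture modeling". Retention and time to drop-out are analysed as outcomes in their own right.

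**The concern.** A side effect is ordinarily a reason to stop a drug, not to stop measuring the patient. Here the two are joined. The arms carry zero, one or two active drugs, so exits for side effects may differ by arm. Exits for non-compliance or protocol violation may follow cocaine use.

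H1 is a test of differential change over time. It leans on the later weeks, and those are the weeks that termination removes. Abstinence in the last two weeks depends on them entirely. The mixed model can use only what was seen before exit. The pattern-mixture analysis is conditional, and it must assume later values that continued sampling would partly observe. Data not collected during the trial cannot be recovered at the analysis.

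**Working it through.** **1. Text check.** I looked for any provision for cocaine-use data after termination.

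| Place | What it offers | Schedules urine or SUR after termination? |
|---|---|---|
| 4.1, two contact persons | A way to reach people | No |
| 6.4, ropinirole hold at 2 mg/d | A dose change in one arm | No |
| 7.2.3, treatment visits | Urine alongside dosing | Not stated for terminated participants |
| 7.2.5, week 9 visit | Fixed time point | Not stated for terminated participants |
| 8, schedule, including Weekly Locator | Weeks to 10 | No such column |
| 9.2, SAE definition | Mentions planned follow-up | No visit or measure attached |

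**2. Arm size.** Four equal arms give 200/4 = 50. If 10% to 25% were terminated (assumed), that is 0.10 × 50 = 5 to 0.25 × 50 = 12.5 participants per arm.

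**3. Bias in the late-week proportion of non-use.** Every input from here to step 5 is assumed. Bias is the estimated arm difference without post-termination data minus the estimate with full follow-up. The gap is the difference in proportion of non-use between terminated and continuing participants, set at 0.3. If the gap opens only after exit, bias should be roughly the difference in termination rates times the gap:

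- 15% v 5%: 0.10 × 0.3 = 0.030
- 25% v 10%: 0.15 × 0.3 = 0.045
- 25% v 0%: 0.25 × 0.3 = 0.075

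A simulation then fitted a logistic random-intercept model with linear week, arm and their interaction. It used three urines a week for 10 weeks, baseline non-use 0.5, exit after weeks 3 to 6, and the mean of 3 runs with 3,500 per arm. Monte Carlo error is about 0.004. Paired entries are for random-intercept SD 1.2 / 1.8.

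| Terminated | Gap visible before exit | Gap only after exit |
|---|---|---|
| 10% v 10%, equal gap (SD 1.2 only) | 0 within error | 0 within error |
| 15% v 5% | 0.008 / 0.004 | 0.037 / 0.036 |
| 25% v 10% | 0.013 / 0.009 | 0.047 / 0.057 |
| 25% v 0% (extreme) | 0.018 / 0.015 | 0.085 / 0.084 |
| 15% v 15%, gaps 0 and 0.3 | −0.013 / −0.010 | −0.052 / −0.051 |

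The last column is of the size that the hand formula predicts. The last row shows that equal rates do not protect if the reasons differ by arm. The sign reverses if the gap reverses.

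**4. Effect on the H1 interaction.** This is the shift in the log odds ratio from week 1 to week 10, divided by the model standard error at 50 per arm (0.285 / 0.314).

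| Terminated | Visible before exit | Only after exit |
|---|---|---|
| 15% v 5% | 0.045/0.285 = 0.16; 0.028/0.314 = 0.09 | 0.220/0.285 = 0.77; 0.259/0.314 = 0.82 |
| 25% v 10% | 0.067/0.285 = 0.24; 0.047/0.314 = 0.15 | 0.280/0.285 = 0.98; 0.352/0.314 = 1.12 |

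**5. What continued collection would recover.** If a random half of terminated participants keep giving samples, the late-week bias for the 15% v 5% and 25% v 10% cases falls to 0.001 to 0.004 (visible before) and 0.017 to 0.025 (only after). A random half is a favourable assumption. A separate run (SD 1.2, gap only after exit) set the gap at 0.15 in those who return and 0.45 in those who do not. It left 0.022 (15% v 5%) and 0.038 (25% v 10%). The same run with random return left 0.015 and 0.020.

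**6. Cost in prize draws.** Table 1 of section 6.5 gives week w three visits of w draws plus 5 bonus draws, that is 3w + 5. Weeks 1 to 3: 8 + 11 + 14 = 33. Weeks 4 to 9: 17 + 20 + 23 + 26 + 29 + 32 = 147. The total is 180, as the table states.

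**The case against.** Several points on the other side stand.

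- **The section is permissive.** It calls termination appropriate and does not require it. A reader might infer that follow-up is forbidden, or that terminated participants leave the intent-to-treat sample. The documents support neither reading. These participants stay in the sample, their earlier data stay in the model, and their drop-out is analysed. Only the later outcomes are lost.
- **Its reach is narrow.** It governs termination decided by staff. Participants who simply stop attending are not covered, rewording will not bring them back, and the documents give no split between the two.
- **There is some mitigation.** The ropinirole hold may reduce side-effect exits in the most exposed arm, although it offers no off-drug follow-up. The SAP already plans for attrition.
- **Some text is not supplied.** The SAP defines cocaine use through Sect. B.3.2.5.ii, which may say how uncollected urines are scored. So specimens and reports would not be collected, but whether the analysed endpoint is missing cannot be said.
- **A careless remedy would alter H1.** Retention is part of H1. If people stopped for side effects kept attending and counted as retained, an arm with more such stops would look better on retention than under the present text. The remedy must define the drop-out event.

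None of this supplies the missing collection.

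**Conclusion.** The gap holds: the plan has no route by which a participant stops drug and goes on giving cocaine-use data. It is a worthwhile, inexpensive improvement, not a demonstrated flaw in the result.

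A reader might infer from the larger figures that the trial's estimate is biased by about a standard error. The documents do not support that. They give no termination rates, no gap and no direction. The H1 shift of roughly 0.8 to 1.1 standard errors needs unequal termination rates together with a 0.3 gap that appears only after exit. If the gap is visible beforehand, the shift is about 0.1 to 0.25 standard errors, and the late-week bias of 0.004 to 0.013 is close to simulation error. With equal rates and equal gaps it is zero. Without later data the trial cannot tell which case applies, and that is the reason to collect them.

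**What to change.** Reword section 7.2.4, Early Termination, as follows.

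1. The listed reasons stop study medication.
2. The scheduled urine tests and SUR continue through the end of treatment, with weekly CBT and attendance draws offered, for every randomised participant who is willing and able and for whom attendance is safe.
3. These data enter the intent-to-treat analysis of cocaine use.
4. The date and reason for stopping drug are recorded separately from the date and reason for leaving the study.
5. For the retention and time-to-drop-out analyses, a participant stopped under this section counts as a drop-out (non-completer) on the drug-stop date, even if still attending. Study exit is reported separately as supportive. This keeps the H1 retention outcome as now planned.

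The cost is protocol wording, extra date and reason fields, and the off-drug visits, CBT sessions and draws. Someone who stops after week 3 and attends every visit through week 9 could earn at most 147 of the 180 draws. No new procedure is needed, because urine and SUR are already scheduled three times a week. Recovery will be partial, since those stopped for non-compliance or serious illness are the least likely to return. It will be less than the random-half figures suggest if those who return differ less from continuing participants than those who do not.

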7.2.5 END OF STUDY VISIT (WEEK 9)

At week 9, participants will be administered end of study assessments and given appropriate referrals to alternative treatment facilities in the area.

8. ASSESSMENT SCHEDULE

STUDY 64		Admit week	1	2	3	4	5	6	7	8	9	10
Forms												
Study 64 consent form and quiz		X										
Medication information sheet		X										
Weekly Locator		X	X	X	X	X	X	X	X	X	X	X
Con Med		X	X	X	X	X	X	X	X	X	X	X
SUR (3xwk)		X	X	X	X	X	X	X	X	X	X	X
AIMS		X	X	X	X	X	X	X	X	X	X	X
AE		X	X	X	X	X	X	X	X	X	X	X
BDI-2		X										X
BSCS		X										X
SHAPS		X										
URICA		X										
DTCQ		X										
OCDUS		X	X	X	X	X	X	X	X	X	X	X
NART-2		X										
Shipley - 2		X										
Computerized Tests												
IGT-repeat version		X			X		X		X		X	
Risky Decision Making		X			X		X		X		X	
Continuous Performance Test		X			X		X		X		X	
Progressive Ratio (PR)		X			X		X		X		X	
Cocaine Stroop		X			X		X		X		X	
Reversal Learning		X			X		X		X		X	
Activities												
Blood draw				X		X		X		X		X
Preg				X		X		X		X		X
EKG		X		X		X		X		X		X
Vitals		X	X	X	X	X	X	X	X	X	X	X
BAL (3x/wk)		X	X	X	X	X	X	X	X	X	X	X
Urine rapid Test (3x/wk)		X	X	X	X	X	X	X	X	X	X	X
Fishbowl		X	X	X	X	X	X	X	X	X	X	X

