4. DESCRIPTION OF STUDY POPULATION

4.1 INCLUSION CRITERIA

1. be between 18 and 55 years of age
2. meet DSM-IV criteria for current cocaine dependence
3. have at least 1 positive urine benzoylecgonine (BE) specimen (> 300 ng/mL) during intake
4. be in acceptable health on the basis of interview, medical history and physical exam
5. be able to understand the consent form and provide written informed consent
6. be able to provide the names of at least 2 persons who can generally locate their whereabouts.

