4.2 EXCLUSION CRITERIA

1. current DSM-IV diagnosis of any psychoactive substance dependence other than cocaine or nicotine
2. have a DSM-IV axis I psychiatric disorder or neurological disease or disorder requiring ongoing treatment and/or making study participation unsafe
3. have cognitive impairment due to non-substance related factors (e.g., history of stroke, transient ischemic attacks, mental retardation, epilepsy, head injury)
4. significant current suicidal or homicidal ideation
5. medical conditions contraindicating levodopa/carbidopa or ropinirole pharmacotherapy (e.g., evidence of any movement disorder, clinically significant pulmonary disease, cardiovascular disease, liver or kidney disease, seizure disorder)
6. taking CNS active concomitant medications
7. taking medications known to have significant drug interactions with the study medication(s) (e.g., CYP P-450-2D6 inhibitors, such as tamoxifen, iron salts, pyridoxine, monoamine oxidase inhibitors, phenothiazines, selegiline, anesthetics)
8. currently or recently (last 3 months) treated for substance use or another psychiatric condition
9. having conditions of probation or parole requiring reports of drug use to officers of the court
10. impending incarceration
11. pregnant or nursing for female patients
12. inability to read, write, or speak English
13. having plans to leave the immediate geographical area within 3 months
14. unwillingness to sign a written informed consent form.

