6.4 MEDICATION DISPENSING

At each clinic visit (MWF) subjects will be administered the medication at the dispensing window and given take-home doses for intervening days. Riboflavin (50mg) will be added to the medication (and placebo) capsules and used as a marker to monitor compliance. We will use a double-dummy method involving a matched placebo for each of the two medications. Placebo capsules will be identical in size, color, coating and shape. Participants in all conditions will take the same number of capsules at the same scheduled times (morning/evening) per day throughout treatment. Participants in the single medication condition will take one matching placebo twice per day, at the same time they take their active study medication. Participants in the placebo group will take two matching placebos twice per day. This method, along with additional strategies used in our clinic to protect the integrity of blindness, will be applied.

Placebo + placebo

	Wk1	Wk2	Wk3	Wk4	Wk5	Wk6	Wk7	Wk8	Wk9	Wk10
L-dopa/carb	0	0	0	0	0	0	0	0	0	0
ropinirole	0	0	0	0	0	0	0	0	0	0
Total										
I-dopa/carb	0mg									
ropinirole	0 mg									
Morning dose	1 capsule placebo ; 1 capsule placebo									
Evening dose	1 capsule placebo ; 1 capsule placebo									
Total pills	4	4	4	4	4	4	4	4	4	4
	Run-up			Maintenance						Run-down

Comments: High dose condition (l-dopa/carbidopa + ropinirole 4 mg/d) has option to hold ropinirole dose at 2 mg/d if tolerability issues. Blood pressure monitoring at every clinic visit.

Levodopa-carbidopa 800/200 mg/d + placebo

	Wk1	Wk2	Wk3	Wk4	Wk5	Wk6	Wk7	Wk8	Wk9	Wk10
L-dopa/carb	200/50 x 2	400/100 x 2	400/100 x 2	400/100 x 2	400/100 x 2	400/100 x 2	400/100 x 2	400/100 x 2	400/100 x 2	200/50 x 2
ropinirole	0	0	0	0	0	0	0	0	0	0
Total L-dopa/carb	400/100 0 mg	800/200 0 mg	400/100 0 mg							
Morning dose	1 capsule containing 2-200/50 tablets; 1 capsule placebo									
Evening dose	1 capsule placebo; 1 capsule placebo	1 capsule containing 2-200/50 tablets; 1 capsule placebo	1 capsule containing 2-200/50 tablets; 1 capsule placebo	1 capsule containing 2-200/50 tablets; 1 capsule placebo	1 capsule containing 2-200/50 tablets; 1 capsule placebo	1 capsule containing 2-200/50 tablets; 1 capsule placebo	1 capsule containing 2-200/50 tablets; 1 capsule placebo	1 capsule containing 2-200/50 tablets; 1 capsule placebo	1 capsule containing 2-200/50 tablets; 1 capsule placebo	1 capsule placebo; 1 capsule placebo
Total pills	4									

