9. SAFETY ASSESSMENT

9.1 DEFINITION OF AE

An adverse event (AE) is defined as any unfavorable and unintended sign including an abnormal laboratory finding, symptom or disease associated with the use of a medical treatment or procedure, regardless of whether it is considered related to the medical treatment or procedure, that occurs during the course of the study.

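### The schedule has no pregnancy test or blood draw before first dose, and the protocol neither names an intake result as the substitute nor limits its age

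*Protocol*

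**What the plan says.** Section 4.2 of the Protocol excludes anyone "pregnant or nursing for female patients" (criterion 11). Criterion 5 excludes conditions that contraindicate the study drugs, with examples that include "clinically significant pulmonary disease, cardiovascular disease, liver or kidney disease, seizure disorder". Neither criterion names a test or a date by which status must be known. Inclusion criterion 4 in Section 4.1 asks that a participant "be in acceptable health on the basis of interview, medical history and physical exam"; no laboratory result is mentioned.

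In Section 8 the blood row reads "Blood draw X X X X X", and the pregnancy row carries the same five marks. Section 6.4 gives the levodopa/carbidopa titration for weeks 1 and 2 as "L-dopa/carb 200/50 x 2 400/100 x 2", so active drug begins in week 1.

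Section 7.1 sends every candidate first through a separate general evaluation protocol, whose content is not in these documents. Section 9.1 counts as an adverse event "any unfavorable and unintended sign including an abnormal laboratory finding". The early-termination list (the second section numbered 7.2.4) does not mention pregnancy.

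**The concern.** Two entry criteria concern states that history and examination can miss: early pregnancy, and liver or kidney disease without symptoms. On the trial's own schedule, the first objective look at either comes after dosing has begun. Men and women aged 18 to 55 are recruited, and Section 9.2 lists a congenital anomaly in offspring among the serious adverse events, so the protocol itself treats exposure in pregnancy as important.

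The second stake is attribution. If an abnormal laboratory value is first seen at week 2 and no pre-dose value has been designated, nobody can say for that participant whether it was present at entry or arose on treatment.

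A test at intake would help with both, but only if the protocol relies on it and limits its age. A negative pregnancy result loses its value with time, and no maximum interval from intake to first dose is given.

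**Working it through.** The plan gives no figure to reproduce. The check sets the schedule beside the dosing tables.

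1. **Columns.** The header row is "STUDY 64 Admit week 1 2 3 4 5 6 7 8 9 10". Counting fields from the row label, the admit week is field 3, week 1 is field 4 and week 2 is field 5.
2. **Blood draw and pregnancy rows.** In each, the first mark is in field 5 and the rest are in fields 7, 9, 11 and 13. These are weeks 2, 4, 6, 8 and 10. Fields 3 and 4 are empty.
3. **Comparison rows.** The EKG row has the same five even-week marks plus one in field 3. Vitals, breath alcohol and the rapid urine test are also marked at the admit week. The pregnancy and blood rows are the only two in the whole table without an admit-week mark.
4. **The admit week precedes dosing.** Section 7.2.4 on compensation places the behavioral tasks at weeks -1, 3, 5, 7 and 9. Section 8 marks the same tasks at the admit week and weeks 3, 5, 7 and 9. The admit week is therefore week -1.
5. **First dose.** The Section 6.4 tables give 400/100 mg/d of levodopa/carbidopa in week 1 in all three active arms. In week 2 this rises to 800/200 mg/d, and ropinirole 2 mg starts in the two combination arms.
6. **Gap.** The schedule names no visit day. If the first dose is given on the Monday of week 1, the Monday, Wednesday and Friday visits of week 2 fall 7, 9 and 11 days later. The first scheduled test thus follows about one week or more of dosing.
7. **Count.** Scheduled pregnancy tests before first dose: 0 of 5. Scheduled blood draws before first dose: 0 of 5.
8. **Arm totals.** With 200 randomized equally to four arms, 200 × 3/4 = 150 are assigned levodopa/carbidopa and 200 × 2/4 = 100 are assigned ropinirole. Both totals include men.
9. **Could intake fill the gap?** Sections 4.1, 4.2 and 7.1 were read for three things: a named pregnancy test or blood chemistry at intake, a maximum age for the result, and a statement that it serves as baseline. None of the three appears.

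**The case against.** The strongest reply is that screening belongs to the intake protocol, which is not in these documents. Every candidate passes through it. The abstract expects 320 to start intake and 200 to be randomized, and inclusion criterion 3 shows that urine is collected there. A reader might infer from Section 8 that exclusions 5 and 11 go unchecked before dosing. The documents do not support that; they neither confirm nor rule out intake testing.

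Nor does the table list every pre-randomization check. It has no row for the physical examination, the medical history, the DSM-IV diagnosis or the Barratt score that the urn randomization needs. An empty admit-week cell is therefore weak evidence that no test is done. This objection stands, and it limits the point to what this protocol specifies. It does not supply the missing reliance on intake or the missing age limit.

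Three further objections also stand:

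- The analytes in the blood draw are not stated, so reading it as liver and kidney chemistry is an assumption.
- A reader might infer that the missing baseline blurs the comparison of laboratory adverse events between arms. The SAP plans no such comparison. In a randomized trial with a concurrent placebo arm, pre-existing abnormalities balance in expectation. What is lost is attribution for the individual, plus some noise.
- A reader might infer that Section 4.2, the early-termination list and Section 8 contradict one another about pregnancy. They do not. The termination list is silent, and its general grounds might be stretched to cover a positive test.

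**Conclusion.** The point holds as a gap in specification with a safety consequence. Study 64 schedules no pregnancy test and no blood draw before first dose. It does not say that intake supplies them, sets no limit on the age of an intake result, and designates no pre-dose laboratory baseline. As written, a woman pregnant at randomization could take study drug for about a week or more before the first scheduled test. An intake test, if one exists, reduces that chance. With no age limit it does not establish her status at randomization.

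The number of participants at risk is unknown, because the documents give no sex split and no rate of pregnancy or unrecognized organ disease. The totals of 150 and 100 describe arm sizes and should not be read as numbers at risk.

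The conclusion assumes that the column positions in Section 8 are as read above. The part about exclusion 5 also assumes that the blood draw includes liver and kidney chemistry. The change is worth making because it is cheap and useful whether or not intake tests.

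**What to change.** - **Section 8, pregnancy:** add an admit-week mark to the pregnancy row and run the test on the urine already collected that week. State in Section 4.2 that a negative result is required before randomization.
- **Section 8, blood:** either add an admit-week draw, or state that the general-evaluation result, taken within a set number of days before first dose, is the check for exclusion 5 and the baseline for laboratory adverse events. List the analytes.
- **Section 7.2.4, Early Termination:** add that a positive pregnancy test on treatment stops study drug.

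The cost is one urine pregnancy test per woman, one or two marks in the table and a few sentences. No extra draw is needed if a recent intake result is used. The downside is a few late screen failures among people who have already completed intake.
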